5.1.2.1 Monotherapy Dose Escalation (Preliminary Safety Cohorts and Part A)

Up to approximately 34 participants may be treated during the monotherapy dose escalation (Preliminary Safety Cohorts and Part A).

Expected dose levels for monotherapy dose escalation (Preliminary Safety Cohorts and Part A) are provided in Table 5.1.2.1-1. All participants treated with BMS-986226 monotherapy are recommended to receive premedications, as described in Section 7.1, in order to reduce the risk of infusion-related reactions.

Preliminary Safety Cohorts

The Preliminary Safety Cohorts will evaluate the safety of BMS-986226 following monotherapy administration of 2 dose levels, 2 mg and 8 mg.

A single new participant per cohort will be administered an IV BMS-986226 as follows:

- BMS-986226 2 mg Q4W in 4-week cycles for up to 24 weeks of study treatment
- BMS-986226 8 mg Q4W in 4-week cycles for up to 24 weeks of study treatment

For the purpose of guiding dose escalation, dose-limiting toxicities (DLTs) will be defined based on the incidence, intensity, and duration of AEs for which no clear alternative cause is identified. The DLT period will be 28 days (4 weeks) in the Preliminary Safety Cohorts. Any toxicities that occur beyond the 4-week DLT period will also be considered in dose-level decisions. For the purpose of participant management, any AE that meets DLT criteria (Section 7.3.2), regardless of the cycle in which it occurs, will lead to discontinuation of study treatment. Participants who discontinue study treatment during the 4-week DLT evaluation period for reasons other than a DLT may be replaced with a new participant at the same dose level. AEs will be graded according to the National Cancer Institute (NCI) Common Terminology Criteria for Adverse Events (CTCAE) v4.03²⁷.

Once the safety (during the 4 weeks DLT period) of 2 mg and 8 mg of BMS-986226 has been established in a single, independent participant per dose, Part A will start.

Additional participants may be enrolled in the Preliminary Safety Cohorts per dose level as early as 5 days after the first participant is treated at each dose level to gather additional information on the safety, PK, and PD profile.

Intra-participant dose escalation is only allowed in the Preliminary Safety Cohorts as follows:

- Once the observation period of 4 weeks for 8 mg is completed, participant(s) treated at 2 mg may be offered the possibility to dose escalate at 8 mg.
- Once the DLT period of 5 weeks for 25 mg is completed, participant(s) treated at 2 mg that escalated to 8 mg or participant(s) treated with 8 mg may be offered the possibility to dose escalate at 25 mg

The decision to dose escalate may be allowed in select participants after discussion and agreement with the BMS Medical Monitor/Study Director (or designee), as long as the participant is tolerating treatment.

The decision to treat a participant with additional cycles of study treatment (up to a maximum of 24 weeks), will be based on safety, tolerability, and tumor assessment Q8W (± 1 week) prior to dose administration in the next cycle.

Part A

Dose escalation decisions in Part A of the study will be guided by Bayesian Logistic Regression Model (BLRM). Each participant will be administered IV doses of BMS-986226 per the cohort assignment as follows:

- 25 mg flat dose Q4W in 4-week cycles for up to 24 weeks of study treatment
- 80 mg flat dose Q4W in 4-week cycles for up to 24 weeks of study treatment
- 200 mg flat dose Q4W in 4-week cycles for up to 24 weeks of study treatment
- 400 mg flat dose Q4W in 4-week cycles for up to 24 weeks of study treatment
- 800 mg flat dose Q4W in 4-week cycles for up to 24 weeks of study treatment

A sentinel participant will be used for all cohorts of monotherapy in Part A and combination therapy in Parts B and C. The first participant in each cohort will receive the Cycle 1 Day 1 dose of study treatment and be observed for 5 days before additional participants (ie, Participant 2 onward) in that cohort receive study treatment.

The decision to treat a participant with additional cycles of study treatment (up to a maximum of 24 weeks), will be based on safety, tolerability, and tumor assessment Q8W (± 1 week) prior to dose administration in the next cycle.

Planned dose levels may be modified or intermediate dose levels added guided by the BLRM analysis with consideration of all available safety, PK, and PD data.

Once the safety (during the DLT evaluation) of a dose level has been established, additional participants (up to a total of 12) may be added at that dose level to better characterize the safety, PK, and PD profile.

Dose Escalation Decisions for Part A

The dose-escalation phase of the study will evaluate the safety and tolerability of BMS-986226 monotherapy based on DLTs using a BLRM model.

During the dose-escalation phase, a set of approximately 3 participants will be treated initially at each specified dose level. Cohort tolerability assessment and subsequent dose recommendation will occur when at least 2 evaluable participants within a cohort have completed a 5-week DLT period. Any toxicities that occur beyond the 5-week DLT period will be accounted for in making dose level decisions and/or dose level modifications.

If the potential DLT occurring in the third evaluable participant regarding the specific dose level does not influence the dose recommendation by BLRM, the next dose level may proceed without waiting for the third participant to complete the corresponding DLT observation period after discussion and agreement between the Sponsor and investigators. Continuous re-assessment of dose recommendation, by BLRM in the monotherapy escalation phase, will be carried out for each dose level. Planned dose levels for dose escalation are provided in Table 5.1.2.1-1. Planned dose levels may be modified, or additional intermediate dose levels added, based upon the BLRM

analysis. Once the safety (during the DLT evaluation) of a monotherapy dose level has been established (Preliminary Safety Cohorts and Part A), additional participants (up to 12 total) may be added at that dose level to better characterize the safety, PK, and PD profile.

Dose Level	BMS-986226		
1	2 mg (Preliminary Safety Cohorts)		
2	8 mg (Preliminary Safety Cohorts)		
3	25 mg (Part A)		
4	80 mg (Part A)		
5	200 mg (Part A)		
6	400 mg (Part A)		
7	800 mg (Part A)		

 Table 5.1.2.1-1:
 Dose Escalation (Preliminary Safety Cohorts and Part A)

Dose-limiting Toxicities in Part A

For the purpose of guiding dose escalation, DLTs will be defined based on the incidence, intensity, and duration of AEs for which no clear alternative cause is identified. The DLT period will be 35 days (5 weeks) in Part A. Any toxicities that occur beyond the 5-week DLT period will also be considered in dose-level decisions.

For the purpose of participant management, any AE that meets DLT criteria (Section 7.3.2), regardless of the cycle in which it occurs, will lead to discontinuation of study treatment. Participants who withdraw from the study during the DLT evaluation period for reasons other than a DLT may be replaced with a new participant at the same dose level. The incidence of DLT(s) during the DLT evaluation period will be used in dose escalation decisions in Part A and guide dose recommendations in Parts B and C. AEs occurring after the 5-week DLT evaluation period will be considered for the purposes of defining any BLRM recommended dose upon agreement between the Sponsor, Medical Monitor/Study Director (or designee), and investigators, if the AEs are determined to have no clear alternative cause and are not related to disease progression.

AEs will be graded according to the National Cancer Institute (NCI) Common Terminology Criteria for Adverse Events (CTCAE) v4.03.²⁷

5.1.2.2 BMS-986226 and Nivolumab Combination Therapy Cohort (Parts B1 and B2)

The purpose of combination cohort with nivolumab is to gather safety, tolerability, PK, and PD information regarding the administration of BMS-986226 in combination with nivolumab 480 mg flat dose Q4W. Part B1 aims to determine the kinetics of ICOS receptor downmodulation and reexpression (and/or change in selected target engagement/PD) following administration of BMS-986226 Q12W in combination with nivolumab 480 mg administered Q4W for a duration of 2 years. Continuous evaluation of toxicity events in the combination cohort will be performed throughout the enrollment. All participants treated with BMS-986226 in combination with nivolumab are recommended to receive premedications, as described in Section 7.1, in order to reduce the risk of infusion-related reactions.

Up to 3 different dose levels of BMS-986226 will be tested in Part B1, as determined by safety, PK and PD data. The starting dose level used in combination with nivolumab (Part B) will be one dose level lower than a monotherapy (Part A) dose that has cleared the DLT period. At each dose level, approximately 6 evaluable participants will be treated. A sentinel participant will be enrolled in Part B1 (BMS-986226 Q12W + nivolumab 480 mg Q4W) and observed for 5 days before additional participants in Parts B1 at the same dose level receive study treatment.

Part B2 (BMS-986226 Q4W + nivolumab 480 mg Q4W) will be opened at dose levels evaluated in at least one participant in Part B1. Approximately 6-12 evaluable participants will be treated per cohort, if enrolled, to better characterize safety, PK, and PD of the combination. For instance, Part B2 will begin enrollment if the re-expression of ICOS on circulating T cells is observed 4 weeks after the first dose of BMS-986226 in Parts A or B1. Part B2 would therefore be utilized to provide a more granular assessment of safety and PD of BMS-986226. More than 1 dose level (no more than 3 different dose levels) may be enrolled, should additional safety, PK, and PD data be needed.

Once the safety (during the DLT evaluation) of a combination of BMS-986226 and nivolumab has been established and a recommended BMS-986226 dose regimen has been selected for Part D, then additional participants (up to 6 additional evaluable participants) may be treated at the recommended dose to better characterize the safety, PK, and PD profile.

5.1.2.3 BMS-986226 and Ipilimumab Combination Therapy Cohort (Parts C1 and C2)

The purpose of combination cohort with ipilimumab is to gather safety, tolerability, PK, and PD information regarding the administration of BMS-986226 in combination with ipilimumab at 3 mg/kg Q4W. Part C1 aims to determine the kinetics of ICOS receptor downmodulation and re-expression (and/or change in selected target engagement/PD () following administration of BMS-986226 Q12W in combination with ipilimumab administered Q4W for a duration of 2 years. Continuous evaluation of toxicity events in the combination cohort will be performed throughout the enrollment. All participants treated with BMS-986226 in combination with ipilimumab are recommended to receive premedications, as described in Section 7.1, in order to reduce the risk of infusion-related reactions.

Up to 3 different dose levels of BMS-986226 will be tested in Parts C1, as determined by safety, PK and PD data. The starting dose level used in combination with ipilimumab (Part C) will be one dose level lower than a monotherapy (Part A) dose that has cleared the DLT period. At each dose level, approximately 6 evaluable participants will be treated, where a sentinel participant will be enrolled in Part C1 (BMS-986226 Q12W + ipilimumab 3mg/kg Q4W and observed for 5 days before additional participants in Parts C1 at the same dose level receive study treatment.

Part C2 (BMS-986226 Q4W + ipilimumab 3 mg/kg Q4W) will be opened at dose levels evaluated in at least one participant in Part C1. Approximately 6-12 evaluable participants will be treated per

dose cohort, if enrolled, to better characterize safety, PK, and PD of the combination. For instance, Part C2 will begin enrollment if the re-expression of ICOS on circulating T cells is observed 4 weeks after the first dose of BMS-986226 in Part A or C1. Part C2 would therefore be utilized to provide a more granular assessment of safety and PD of BMS-986226. More than 1 dose level (no more than 3 different dose levels) may be enrolled, should additional safety, PK, and PD data be needed.

Once the safety (during the DLT evaluation) of a combination of BMS-986226 and ipilimumab has been established and a recommended BMS-986226 dose regimen has been selected for Part E, then additional participants (up to 6 additional evaluable participants) may be treated at the recommended dose to better characterize the safety, PK, and PD profile.

Dose-limiting Toxicities in Combination Cohorts (Parts B and C)

For the purpose of ensuring safety, DLTs will be defined based on the incidence, intensity, and duration of AEs for which no clear alternative cause is identified. The DLT period will be 35 days (5 weeks) in Parts B and C.

For the purpose of participant management, any AE that meets DLT criteria (Section 7.3.2), regardless of the cycle in which it occurs, will lead to temporary hold of study treatment.

Participants who withdraw from the study during the DLT evaluation period for reasons other than a DLT may be replaced with a new participant at the same dose level.

Re-challenge of participants experiencing a DLT will be evaluated on a case-by-case basis, once the AE returns to baseline or Grade 1, after specific consultation and agreement between the investigator and BMS Medical Monitor/Study Director (or designee) in settings where benefit/risk justify re-administration of study treatment (see Section 7.3.5).

AEs will be graded according to the NCI CTCAE v4.03.²⁷

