5.1.3 Follow-up

5.1.3.1 Safety Follow-up

Upon completion of 24 weeks of study treatment for Part A (or up to a maximum of 48 weeks if applicable) or 2 years for Parts B, C, D, and E, once the decision is made to discontinue the participant from study treatment (e.g., at end of treatment [EOT]), all participants will enter the safety follow-up period.

For participants who complete all scheduled cycles of therapy, the EOT visit will be the same as the last scheduled and completed on-treatment visit and the start of the Week 1 safety follow-up visit. For participants who do not complete all scheduled cycles of study treatment, the EOT visit will be the most recent on-treatment visit (with all available safety and response data), does not need to be repeated, and will be considered the start of the safety follow-up visit.

After the EOT visit, all participants will be evaluated for any new AEs for at least 100 days after the last dose of study treatment. Follow-up visits to monitor for AEs should occur at Days 30, 60, and 100 after the last dose or on the date of discontinuation (\pm 7 days). All participants will be required to complete the 3 clinical safety follow-up visits regardless of whether or not they start new anti-cancer treatment, except those participants who withdraw consent for study participation.

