7.3.2 BMS-986226 Dose-limiting Toxicities

For the purpose of guiding dose escalation, DLTs will be defined based on the incidence, intensity, and duration of AEs for which no clear alternative cause is identified. The DLT period will be 35 days (5 weeks).

In the Preliminary Safety Cohorts, participants who have received 1 dose of BMS-986226 and have completed, or who discontinued due to a DLT in the 4-week DLT period, will be considered as DLT-evaluable participants for BMS-986226 monotherapy.

In Part A, participants who have received 2 doses of BMS-986226 and have completed, or who discontinued due to a DLT in the 5-week DLT period, will be considered as DLT-evaluable participants for BMS-986226 monotherapy.

In Parts B, C, D and E, participants receiving either 1 dose of BMS-986226 or 2 doses of either nivolumab or ipilimumab, or participants who discontinued due to a DLT in the 5-week combination treatment DLT period, will be considered as DLT-evaluable participants for combination treatment. Participants who withdraw from the study during the DLT evaluation period or have received less than 2 doses for reasons other than a DLT in the monotherapy (Part A) or 1 dose in combination therapy (Parts B, C, D, E), will not be considered as DLT-evaluable participants in Part A, who are dose delayed during the DLT evaluation period for reasons other than a DLT could be considered as DLT-evaluable participants if they receive at least 2 doses of therapy.

For the purpose of participant management, any AE that meets DLT criteria, regardless of the cycle in which it occurs, will lead to discontinuation of study treatment (except as defined in Section 7.3.5). Participants who withdraw from the study during the 5-week DLT evaluation period for reasons other than a DLT may be replaced with a new participant at the same dose

level. The incidence of DLT(s) during the 5-week DLT evaluation period will be used in dose escalation decisions through application of the BLRM/BLRM-Copula model. AEs occurring after the DLT period will be considered to enhance the robustness of BLRM/BLRM-Copula prediction, upon agreement between the Sponsor, Medical Monitor/Study Director (or designee), and investigators.

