Participants experiencing a DLT will enter the safety follow-up period of the study. DLTs occurring after the 4-week DLT observation period for the Preliminary Safety Cohorts or 5-week DLT observation period for Parts A, B and C will be accounted for in determining the MAD for the combination part.

AEs will be graded according to the NCI CTCAE v4.03²⁷, as listed below:

A. Hepatic Non-hematological DLT

Any one of the following study treatment-related events will be considered a hepatic DLT:

- Any Grade \geq 3 elevation of AST, ALT, or total bilirubin.
- Grade 2 AST or ALT with symptomatic liver inflammation (eg, right upper quadrant tenderness, jaundice, pruritus).
- AST or ALT > 3× ULN and concurrent total bilirubin > 2× ULN without initial findings of cholestasis (elevated serum alkaline phosphatase [ALP] [eg, findings consistent with Hy's law or FDA definition of potential drug-induced liver injury or potential drug-induced liver injury [p-DILI]). Note that this special category of DLT uses ULN rather than Common Toxicity Criteria (CTC) grade for definition.

B. Non-hepatic Non-hematological DLT

Any of the following events will be considered a non-hepatic non-hematological DLT:

- Any Grade 2 drug-related uveitis or eye pain or blurred vision that does not respond to topical therapy and does not improve to Grade 1 severity ≤ 2 weeks *or* requires systemic treatment.
- Grade 3 drug-related uveitis, pneumonitis, bronchospasm, myocarditis, neurologic toxicity, hypersensitivity reaction, or infusion reaction of any duration will require discontinuation.
- Any Grade 3 or greater nondermatologic, nonhepatic nonhematological study treatment-related toxicity will be considered a DLT, with the following specific exceptions:
 - Grade 3 or Grade 4 electrolyte abnormalities that are not complicated by associated clinical adverse experiences, last \leq 72 hours, and either resolve spontaneously or respond to conventional medical intervention
 - Grade 3 nausea, vomiting, or diarrhea that lasts less than 72 hours (without steroid therapy) and either resolves spontaneously or responds to conventional medical intervention
 - Isolated Grade 3 elevation of amylase or lipase not associated with clinical or radiographic evidence of pancreatitis

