7.3.5 Exceptions to Permanent Discontinuation Criteria

Any drug-related AE occurring at any time that meets DLT criteria as outlined in Section 7.3.2 will require permanent discontinuation. Exceptions to permanent discontinuation are listed in Section 8.1.

Study treatment may be re-initiated in participants experiencing non-life-threatening AEs that meet DLT criteria and that have been resolved to Grade 1 or baseline. Consideration to resume treatment will be made on a case-by-case basis in a discussion between the investigator and BMS Medical Monitor/Study Director (or designee) and approval of the sponsor, taking into account the overall benefit/risk ratio for the individual participant and the following factors:

- A 2-week washout period is required after completing the immune suppressive treatment used to manage the AE (eg, steroids). The AE should not recur/worsen during the washout period.
- Evidence for clinical or radiographic benefit must be present, which can include improvement of physical symptoms (eg, ECOG status, shortness of breath), symptomatic improvement in combination with assessment of SD, or radiographic response.

In the event of recurrence of the AE that met the DLT criteria, study treatment will be permanently discontinued for the participant.

Additionally, consideration to permanently discontinue study treatment for participants with any severe Grade 3 drug-related AE that recurs will be made on a case-by-case basis in a discussion between the investigator and BMS Medical Monitor/Study Director (or designee).

All participants who discontinue IP should comply with protocol-specified follow-up procedures as outlined in Section 5.1.3. The only exception to this requirement is when a participant withdraws consent for all study procedures including post-treatment study follow-up or loses the ability to consent freely (eg, imprisonment or involuntarily incarceration for the treatment of either a psychiatric or physical illness).

If study treatment is discontinued prior to the participant's completion of the study, the reason for the discontinuation must be documented in the participant's medical records and entered on the appropriate Case Report Form (CRF) page.

7.3.6 *Management of Drug-related Infusion Reactions*

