- If symptoms recur, then no further BMS-986226, nivolumab, or ipilimumab will be administered at that visit.
- For future infusions, the following prophylactic premedications are recommended: diphenhydramine 50 mg (or equivalent) and acetaminophen/paracetamol 325 to 1,000 mg should be administered at least 30 minutes before study treatment infusions. If necessary, corticosteroids (up to 25 mg of hydrocortisone or equivalent) may be used.

For Grade 3 or 4 symptoms: Severe reaction, Grade 3: prolonged (eg, not rapidly responsive to symptomatic medication and/or brief interruption of infusion); recurrence of symptoms following initial improvement; hospitalization indicated for other clinical sequelae (eg, renal impairment or pulmonary infiltrates); Grade 4: life-threatening; pressor or ventilatory support indicated.

- Remain at bedside and monitor participant until recovery of the symptoms.
- Immediately discontinue infusion of study treatment.
- Begin an IV infusion of normal saline and treat the participant as follows: recommend bronchodilators, epinephrine 0.2 to 1 mg of a 1:1,000 solution for intramuscular or subcutaneous administration or 0.1 to 0.25 mg of a 1:10,000 solution injected slowly for IV administration, and/or diphenhydramine 50 mg IV with methylprednisolone 100 mg IV (or equivalent), as needed.
- Participant should be monitored until the investigator is comfortable that the symptoms will not recur. Study treatment will be permanently discontinued except for a Grade 3 infusion reaction that returns to Grade 1 in less than 6 hours. Investigators should follow their institutional guidelines for the treatment of anaphylaxis.

In case of late-occurring hypersensitivity symptoms (eg, appearance of a localized or generalized pruritus within 1 week after treatment), symptomatic treatment may be given (eg, oral antihistamine or corticosteroids).

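### The rules after a DLT conflict on safety follow-up, on Grade 3 infusion reactions and on the conditions for resuming treatment

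*Combined protocol and SAP*

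**What the plan says.** The consequence of a DLT is stated in several places.

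- **Section 5.1.2.3, DLT text for Parts B and C:** the event "will lead to temporary hold of study treatment". Re-challenge is considered case by case after recovery, with a reference to Section 7.3.5.
- **Section 5.1.2.1, Preliminary Safety Cohorts and Part A:** treatment is discontinued, with no exception stated.
- **Section 7.3.2, all parts:** treatment is discontinued, with an exception by reference to Section 7.3.5. Shortly afterwards: "Participants experiencing a DLT will enter the safety follow-up period of the study".
- **Section 5.1.3.1:** safety follow-up begins "once the decision is made to discontinue the participant from study treatment".
- **Section 7.3.5:** "Any drug-related AE occurring at any time that meets DLT criteria as outlined in Section 7.3.2 will require permanent discontinuation", followed by "Exceptions to permanent discontinuation are listed in Section 8.1". The section then sets out its own re-start route for resolved, non-life-threatening events. The conditions are a 2-week washout after immune suppression, evidence of benefit and sponsor approval.
- **Section 8.1.1:** the first sentence lets dosing resume once a drug-related DLT has resolved to Grade 1 or baseline. The second requires sponsor agreement and refers to Section 7.3.5.

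On Grade 3 infusion reactions, a Section 7.3.2 bullet says that an "infusion reaction of any duration will require discontinuation". The exception list in the same section removes reactions that return to Grade 1 within 1 hour from the DLT definition. Section 7.3.6 says: "Study treatment will be permanently discontinued except for a Grade 3 infusion reaction that returns to Grade 1 in less than 6 hours".

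**The concern.** These sentences decide whether someone who has had a DLT or a severe infusion reaction is dosed again in a first-in-human study. A site that follows the safety follow-up sentence literally would deny a re-challenge that other sections allow. A site that acts on the first sentence of Section 8.1.1 alone could overlook two of the conditions in Section 7.3.5. For an infusion reaction, the answer depends on which section the investigator opens.

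The infusion-reaction case is not remote. Section 7.3.6 reports Grade 1 or 2 reactions in 7 of 19 monotherapy participants (36.8%), and one Grade 3 hypersensitivity during infusion after the data cut-off.

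**Working it through.** No formula applies; the check sets the rules side by side.

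**(a) Safety follow-up.** The Section 7.3.2 sentence has no exception and no limit to a study part. The exception for Section 7.3.5 belongs to a different sentence, the one on discontinuation. Under Section 5.1.3.1 safety follow-up comes after the decision to discontinue, and no section gives a route from it back to dosing. Taken literally, the sentence contradicts the re-challenge allowed in Section 5.1.2.3, in Section 7.3.2 itself (by exception), in Section 7.3.5 and in Section 8.1.1.

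**(b) Grade 3 infusion reaction, by time to return to Grade 1.**

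| Time to Grade 1 | 7.3.2 bullet | 7.3.2 exception list | 7.3.6 | 7.3.5 |
|---|---|---|---|---|
| 1 hour or less | stop | not a DLT | exempt from permanent stop | not reached if not a DLT |
| over 1, under 6 hours | stop | DLT | exempt from permanent stop, no conditions | permanent stop unless re-start conditions are met |
| 6 hours or more | stop | DLT | permanent stop | permanent stop unless re-start conditions are met |

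A reaction lasting 3 hours shows the problem. It is a DLT, it must stop under the bullet, it may restart only with washout, benefit and approval under Section 7.3.5, and Section 7.3.6 exempts it with none of those conditions.

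**(c) Conditions for resuming.**

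- Section 7.3.1 holds treatment after a DLT. It refers to Section 8.1 for those who must stop and sends the rest to Section 8.1.1.
- Section 8.1 lists Grade 4 drug-related events and several general grounds, but not DLTs as such. A Grade 3 ALT elevation is a DLT in Section 7.3.2 and is not named in Section 8.1.
- That participant can therefore reach the first sentence of Section 8.1.1, where resolution is the only condition.
- Section 7.3.4 sends withheld participants to Section 7.3.5 instead.
- The Section 7.3.5 pointer names only Section 8.1 as the place for exceptions, although Section 7.3.5 grants one itself.

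**Reach.** Sections 7.3.2, 7.3.5, 7.3.6 and 8.1.1 are not restricted by part, so they apply to all of the approximately 234 planned participants. The hold and re-challenge text in Section 5.1.2.3 covers at most 234 − 34 (monotherapy) − 80 (Parts D and E) = 120. Only participants with a DLT or a Grade 3 infusion reaction are touched.

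**The case against.** The best defence is that the protocol read as a whole has one scheme: hold, assess, then discontinue permanently unless Section 7.3.5 applies. Much of that stands.

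- Sections 5.1.2.3 and 7.3.2 both refer to Section 7.3.5, and Sections 7.3.1 and 7.3.4 describe the hold that comes first. A reader might infer that hold in one place and discontinuation in another are opposing rules. The documents do not support that; the difference is one of default wording.
- The safety follow-up sentence most naturally describes where discontinued participants go. It contradicts the re-challenge route but does not abolish it.
- A reader might infer that Section 8.1.1 allows re-dosing without the sponsor. It does not. Its second sentence requires sponsor agreement, its closing text adds case-by-case consultation, and Section 9 requires immediate safety concerns to be discussed with the sponsor. What could be missed is the washout and the evidence of benefit.
- A reaction lasting between 1 and 6 hours can restart under Section 7.3.5, so Section 7.3.5 does not rule it out. The conflict is that Section 7.3.6 attaches no conditions and the Section 7.3.2 bullet allows no restart.

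The defence does not remove the unqualified follow-up sentence, the three infusion-reaction rules, or the bare first sentence of Section 8.1.1.

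**Conclusion.** Three real conflicts remain, all in text that applies across study parts. They should be corrected because they give different instructions on re-dosing after a DLT or severe infusion reaction. The sponsor-agreement steps limit the harm.

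The effect on discontinuations cannot be sized: the documents give no DLT or re-challenge rate for the combination parts. It would also go too far to infer that the dose-finding is compromised. Under Section 7.3.2 a participant in Parts B or C with one BMS-986226 dose is DLT-evaluable whether later held or discontinued, so DLT counts and the BLRM-Copula input do not change. This takes the 1-hour exception as governing what counts as a DLT, over the any-duration bullet printed under the same DLT heading. Discontinuations are recorded as they occur, so the safety endpoint needs no extra rule.

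One matter is open. Section 5.1.2.1 gives no exception for the Preliminary Safety Cohorts and Part A, while the Section 7.3.5 re-start is not limited by part. The documents do not say which governs.

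**What to change.** 1. **Section 7.3.2, follow-up sentence.** Restrict it: *Participants who permanently discontinue treatment because of a DLT move to safety follow-up.*
2. **Grade 3 infusion reactions.** Set one threshold and use it in the Section 7.3.2 bullet, the Section 7.3.2 exception list and Section 7.3.6. The simplest choice is the existing 1-hour limit, with longer reactions treated as DLTs that may restart only under Section 7.3.5. Section 7.3.6 now bars restart at 6 hours or more, so the sponsor should say whether that upper limit stays.
3. **Resumption.** Make the first sentence of Section 8.1.1 subject to Section 7.3.5. In Sections 7.3.1 and 7.3.4, send DLT holds to Section 7.3.5 and non-DLT holds to Section 8.1.1. Reword the Section 7.3.5 pointer to name its own re-start route as well as the Section 8.1 list.
4. **Default wording.** In Sections 5.1.2.3, 7.3.2 and 7.3.5, state the sequence once: hold first, then permanent discontinuation unless Section 7.3.5 applies.
5. **Monotherapy.** State whether the Section 7.3.5 re-start applies to the Preliminary Safety Cohorts and Part A.

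The cost is a few sentences in a protocol amendment, with no change to visits, sample size or the model. Section 5.1.2.4 already makes Parts D and E wait for a protocol revision, so their rule can be confirmed then.
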